8.4.1. Subsequent visits

All volunteers will be asked to attend as per the Schedule of Visits and Procedures in section 3. On visits other than for vaccination the volunteers will be assessed for local and systemic adverse events, using paper diary cards, interim history, physical examination and blood tests at the time-points indicated in the Schedule of Visits and Procedures (Section 3). Blood will also be taken for assessments of immunogenicity and exploratory immunology analysis. These follow up visits may be done at school (see section 7.9).

8.4.2. MVA85A booster immunisation.

Volunteers in group 5 will be asked to attend between day 56 and day **365** for booster immunisation with MVA85A [volunteers in group 6 will also be asked to attend on this date, but only to provide the samples indicated]. For participants who were enrolled in the trial prior to the COVID-19 lockdown, this boost visit will fall between day 56 and day **365** after enrolment into the trial while for newly enrolled participants, the boost will be done on day 56.

For group 5, before the MVA85A vaccination, the health of the volunteer will be reviewed. Pulse, blood pressure and temperature will be observed and if necessary, a medical history and physical examination may be undertaken to determine need to postpone booster vaccination. For girls, a pregnancy test will be repeated. If the volunteer is well and the pregnancy test is negative MVA vaccination will be administered at 1×10^8 pfu.

Group 5 volunteers will be provided with a diary card and instructed in its use as described above.

Diary cards will be collected two weeks after ChAdOx1 85A and one week after MVA85A as these intervals correspond to the optimal time points for assessing the initial response to the two vaccines.

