Timeline (weeks)*		0		2	4	8-52	9-53	12-56	20-64	32-76
Time windows (days)	-90 to -7		+1	+3	+5	+5	+1	+5	+5	+14
Vaccination, ChAdOx1 85A or BCG		x								
Vaccination, MVA85A [§]						x [§]				
Inclusion/exclusion criteria	x	x								
Review contra- indications	x	x				x				
Informed consent	x									
Medical history	x	(x)	(x)	(x)	(x)	(x)	(x)	(x)	(x)	(x)
Physical examination	x	(x)	(x)	(x)	(x)	(x)	(x)	(x)	(x)	(x)
Vital signs	x	x	x	x	x	x	x	x	x	x
Urinalysis	x									
β-HCG urine test (female only)	x	x				x				
Stool parasitology	x	x	x							x
Anthelminthic treatment									x	
Local & systemic events/reactions		x	x	x	x	x	x	x	x	x
Diary cards provided		x				x				
Diary cards collected				x			x			
Biochemistry (4mL)**/***	x			x		x	x			
HBV, HCV, HIV (6mL)	x									
Haematology: full blood count and storage (2mL)	x		x	x		x	x		x	x
Mansonella perstans (1mL)***	x									x
Malaria RDT/slide; PCR (1mL)	x	x***		x	x	x		x		x
Assessments of immunogenicity and exploratory immunology incl ELISpot (10-20mL)****	x	x	x	x	x	x	x	x	x	x
Gene expression (2mL)	x		x							
Blood vol (mL)	26	10	16	28	5	13	28	5	5	24
Cumulative blood vol (mL)	26	36	52	80	85	98	126	131	136	160

X Event scheduled to occur

(X) If considered necessary, emphasising any complaint or change in medications

* Timeline is approximate only, as exact timings (\pm windows periods) of visits relate to the actual (not intended) date of the previous visit

§ Group 5 only

** Urea & electrolytes, liver function tests

*** Repeated on vaccination day if delay from screening is more than 28 days

**** Exploratory immunology blood volume will be guided by guidelines from Harvard Mass General, where a maximum of 3ml/kg body weight is taken at any one time point and not more than 3ml/kg is taken over any 8 week period (ref http://www.drgreene.com/21_1616.html.) These guidelines have been followed in previous

studies vaccinating adolescents and children with MVA85A (in South Africa [1]). The total blood volume planned is 98 ml over the initial intensive sampling period of 8 weeks. Revision of sample volumes based on weight will only be required for children who weigh less than 33 kg; the average weight of children aged 11 is expected to be greater than 35kg, with greater weights for older children.

a Participants will have variable follow up days depending on whether they were enrolled before or after the COVID 19 lockdown

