6. OBJECTIVES AND OUTCOME MEASURES

Objectives	Outcome Measures	Timepoint(s) of evaluation of this outcome measure
Primary Objective To evaluate the safety and immunogenicity of ChAdOx1 85A – MVA85A prime-boost vaccination in Ugandan adolescents	Actively and passively collected data on adverse events	All Adverse Events (AEs) from day 0-28 post vaccination Serious Adverse Events (SAEs) throughout follow up
	T-cell Interferon- γ ELIspot response to antigen 85A	ELIspot spot-forming counts per 1×10^6 peripheral blood mononuclear cells (PBMCs) at day 14 for groups 1-4 ELIspot spot-forming counts per 1×10^6 peripheral blood mononuclear cells (PBMCs) at day 63 for groups 5 and 6 Area under the curve (AUC) analysis of immunogenicity (days 0-168 for groups 1-4; days 0-168 for groups 5 and 6)
Secondary Objective To further characterise immunogenicity of ChAdOx1 85A – MVA85A prime-boost vaccination in Ugandan adolescents	Antibody response to antigen 85A Exploratory immunology including ELIspot response to BCG, flow cytometry, gene expression, and mycobacterial killing assays	Screening and follow up visits as shown in Schedule of Visits, section 3
Tertiary Objectives 
 
To compare the response to ChAdOx1 85A – MVA85A prime-boost vaccination with the response to BCG revaccination in Ugandan adolescents 
To compare the response to ChAdOx1 85A – MVA85A prime-boost vaccination in Ugandan adolescents with the response in Oxford adults 
To investigate pre-immunisation epidemiological and immunological characteristics associated with the immune response induced by ChAdOx1 85A – MVA85A prime-boost vaccination in Ugandan adolescents 	T-cell Interferon- γ ELIspot response to antigen 85A Antibody response to antigen 85A, exploratory immunology including T cell ELIspots, flow cytometry, gene expression, and mycobacterial killing assays	Primary outcomes for these analyses will be antigen 85A specific ELIspot spot-forming counts per 1×10^6 peripheral blood mononuclear cells (PBMCs) at day 63 from the first vaccination and ELIspot AUC analysis Additional outcomes using data from follow up visits as shown in Schedule of Visits, section 3 Screening and follow up visits as shown in Schedule of Visits, section 3

Table 4. Objectives and Outcome Measures

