8.4.3. Vaccination (D0)

Group 1 adults will be given ChAdOx1 85A at 5×10^9 vp intramuscularly

Group 2 adults will be given ChAdOx1 85A at 2.5×10^{10} vp intramuscularly

Group 3 adolescents will be given ChAdOx1 85A at 5×10^9 vp intramuscularly

Group 4 adolescents will be given ChAdOx1 85A at 2.5×10^{10} vp intramuscularly

Group 5 adolescents will be given ChAdOx1 85A at 2.5×10^{10} vp intramuscularly followed by MVA85A boost at 1×10^8 pfu intramuscularly between day 56 and day 140

Group 6 adolescents will be given BCG revaccination, Serum Institute of India, 0.1 mL intradermally

Following vaccination the following procedures will be undertaken:

In all groups, volunteers will be given a thermometer, tape measure and paper diary card, with instructions on use, along with the emergency 24 hour telephone number to contact the on-call study physician if needed. Volunteers will be instructed on how to self-assess the severity of these AEs. There will also be space on the diary card to self-document unsolicited AEs, and whether medication was taken to relieve the symptoms. Diary cards will collect information on the timing and severity of the following solicited AEs:

Local solicited AEs	Systemic solicited AEs
Pain	Fever
Redness	Feverishness/Chills
Warmth	Joint pains
Itch	Muscle pains
Blistering or ulceration	Fatigue
Swelling of local lymph nodes	Headache
	Malaise
	Abdominal pain
	Chills

Table 6. Solicited AEs as collected on post vaccination diary cards

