11. STATISTICS

This is primarily an exploratory immunogenicity and safety trial with descriptive endpoints.

Adverse events will be listed and summarised by type of AE, frequency, severity and trial group.

The sample size (12 participants for dose escalation and age de-escalation, 60 participants [30 in each arm] for the randomised trial) has been determined by the number of doses of ChAdOx1 85A available for this study. The following are the considerations regarding sample size for the randomised component of the trial. The primary outcome is the IFN- γ ELIspot response to antigen 85A at week 9 which is measured in spot forming counts per 1×10^6 peripheral blood mononuclear cells (PBMCs). Assuming a standard deviation of $0.4 \log_{10}$ sfc/ 1×10^6 PBMC (spot forming counts/ 1×10^6 peripheral blood mononuclear cells) in the peak Ag85A response, our study will have over 80% power to detect a difference of $0.29 \log_{10}$ in sfc/ 10^6 PBMC with $p < 0.05$. This is comparable to the difference that was observed between the response to human adenovirus vectored TB vaccine candidate Aeras 402 alone (Day 14 post Aeras) and Aeras 402 with MVA85A boost (Day 7 post MVA boost) [21], or between BCG (Day 28) and MVA85A alone (Day 7) in UK subjects [62], and hence a reasonable difference to expect between BCG and ChAdOx1 85A-MVA85A (aim 2).

For outcomes that are approximately normally distributed or normalised by log-transformation, differences in means will be presented together with 95% confidence intervals and p-values from unpaired t-tests. For non-normally distributed outcomes, the difference in medians between the two groups will be presented along with its 95% confidence intervals, and p-values from Wilcoxon ranksum tests.

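### Diary cards run 14 days after ChAdOx1 85A or BCG but 7 days after MVA85A, and Section 11 sets no common window, so solicited-AE frequencies are not like for like

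*Combined protocol and SAP*

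**What the plan says.** The primary safety outcome in Section 6 (Table 4) is "All Adverse Events (AEs) from day 0-28 post vaccination", and Section 10.5 applies the 28 days to each vaccination.

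The diary covers only the first part of that window. At day 0, Section 8.4.3 states: "In all groups, volunteers will be given a thermometer, tape measure and paper diary card". The card takes the timing and severity of listed local and systemic events and has space for unsolicited ones. On collection, Section 8.4.2 (MVA85A booster immunisation) states: "Diary cards will be collected two weeks after ChAdOx1 85A and one week after MVA85A as these intervals correspond to the optimal time points". It describes these intervals as the "optimal time points for assessing the initial response to the two vaccines". BCG is not named there. Its 14 days follow from Table 1.2, which groups 5 and 6 share and which collects cards at visit 4 (day 14) and visit 7 (7 days after the boost visit).

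For the second card, the text in Section 8.4.2 reads: "Group 5 volunteers will be provided with a diary card and instructed in its use as described above". Group 6 attends that visit only to give samples. The diary rows of Table 1.2, however, carry no mark restricting the second card to group 5.

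The whole analysis provision for safety in Section 11 is: "Adverse events will be listed and summarised by type of AE, frequency, severity and trial group". It gives no diary window, no per-dose denominator and no rule for combining the two doses of group 5.

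**The concern.** The diary is the instrument that prompts for solicited events. If one vaccine has 14 prompted days and another has 7, the same event starting on day 10 is prompted for in one case and only recalled or volunteered in the other. A table of solicited AEs per dose would then show a lower frequency after MVA85A than after BCG or the prime for a reason that has nothing to do with the vaccines. A table by trial group leans the other way, because group 5 is vaccinated twice and observed twice.

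Safety of the prime-boost regimen is part of the primary objective, and BCG revaccination is the concurrent reference. Readers will set the two columns side by side even though the endpoints are descriptive. As Section 11 stands, they cannot tell how much of a difference comes from observation time.

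**Working it through.** **Inputs.** Visit days and windows are from Table 1.2, taken around the nominal day. The 28-day recording period is from Sections 6 and 10.5. The second card is given to group 5 only, as the text of Section 8.4.2 has it.

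**Diary length per dose (plan's figures reproduced).**
- ChAdOx1 85A or BCG: 14 - 0 = 14 days; with the 3-day window, 11 to 17.
- MVA85A: 63 - 56 = 7 days, and 372 - 365 = 7 for the latest boost; with the 1-day window, 6 to 8.

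These agree with the two weeks and one week in the text.

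**Share of the 28-day window under diary.** 14/28 = 50% after ChAdOx1 85A or BCG; 7/28 = 25% after MVA85A.

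**Contacts inside the window.** Days 2, 14 and 28 after the day-0 vaccine; days 7 and 28 after the boost (84 - 56 = 28; 393 - 365 = 28). The stretch covered by history alone is 28 - 14 = 14 days after the day-0 vaccine and 28 - 7 = 21 days after MVA85A. Days 15-28 are handled alike for all vaccines, so the difference lies in days 8-14.

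**Observation per participant.**

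| | Group 5 | Group 6 |
|---|---|---|
| Diary days | 14 + 7 = 21 | 14 |
| AE-recording days | 2 x 28 = 56 | 28 |

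If group 6 also kept a card from visit 6 to visit 7, as the unmarked table rows would allow, its diary days would be 14 + 7 = 21 as well. The 56 v 28 would remain.

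**Size in a diary-only, per-dose comparison.** The documents give no event rates, so these are assumptions. Let R be vaccine-caused episodes per dose, all starting in the first week, and L background episodes per day. The share of 14-day diary episodes that starts on days 8-14 is 7L/(14L + R).

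| R | 14L = 0.25 | 14L = 0.5 | 14L = 1.0 |
|---|---|---|---|
| 0.5 | 17% | 25% | 33% |
| 1 | 10% | 17% | 25% |
| 2 | 6% | 10% | 17% |

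For example, R = 1 and 14L = 0.25 gives 0.125/1.25 = 10%. By construction these are all background events. The model places no vaccine-caused episode after day 7, and the figures are the share outside a 7-day card, not the share lost to the trial.

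**Size allowing for the day-28 visit.** Let a proportion r of 30 boosted participants have a solicited AE starting on days 8-14, and let visit history capture a proportion c of these. Expected unrecorded cases are 30 x r x (1 - c); r and c are again assumed.

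| r | c = 0 | c = 50% | c = 90% |
|---|---|---|---|
| 2% | 0.6 | 0.3 | 0.06 |
| 5% | 1.5 | 0.75 | 0.15 |
| 10% | 3.0 | 1.5 | 0.3 |

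**The case against.** The case for leaving the plan alone has four parts.

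First, Section 11 calls the endpoints descriptive and plans no per-dose comparison of MVA85A with BCG. This is correct. The imbalance harms only comparisons that the report or its readers choose to make.

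Second, days 8-28 after the boost are not unobserved. All AEs are recorded for 28 days after each vaccination, Table 1.2 reviews local and systemic events at the day-28 post-boost visit, and Section 8.4.1 (Subsequent visits) calls for an interim history. This also stands: what is lost on days 8-14 is prompted recording, not all recording.

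Third, seven days fits the protocol's own expectations. Section 5.4.1 gives 2-3 days for systemic symptoms, and the group 5 holding rules in Section 10.1.1 count onset within 2 or 7 days. A longer card for the newer vector is defensible, with 42 earlier recipients against more than 2500 for MVA85A. This supports a small effect, but it does not make unequal windows comparable.

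Fourth, the documents give collection dates, not the number of days to be completed, so 14 and 7 are nominal. This stands as a caveat.

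A reader might also infer that the collection times were set by the ELISpot peak. Days 14 and 63 are the primary ELISpot timepoints in Section 6, so the idea is plausible. But Section 8.4.2 does not name the assay, and Section 5.1.5 reports a peak only for ChAdOx1 85A (day 14). For MVA85A it reports boosted responses one week later without calling them a peak.

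**Conclusion.** The point holds as a matter of comparability. Per dose, nominal prompted recording after MVA85A is half that after BCG or the prime; per participant, group 5 is observed for longer than group 6. Section 11 does not address either imbalance.

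A reader might go further and conclude that post-boost events are under-ascertained relative to BCG, so that the regimen looks safer than it is. The documents do not support that at arm level. In the by-group summary actually planned, group 5 has the greater AE-recording time (56 v 28 days) and, by the text, the greater diary time (21 v 14 days). Only a diary-based, per-dose comparison leans towards MVA85A.

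The size is probably small. Under the assumed rates, 6% to 33% of 14-day diary episodes would fall outside a 7-day card, all of them background events. The expected number of unrecorded cases among 30 boosted participants runs from 0.06 to 3.0, depending mainly on how well the day-28 history works. This is a minor point, worth acting on because the remedy uses data already collected.

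**What to change.** Add to Section 11:

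- Solicited AEs are tabulated per dose and by vaccine (ChAdOx1 85A, MVA85A, BCG) for onset on days 0-7 after each vaccination. The 14-day card already contains these days, and it records timing.
- Any comparison between vaccines or arms uses this window, with each group 5 dose set against BCG separately. Pooling both doses into one per-participant figure would put 2 x 7 = 14 days against 7.
- The number of cards collected at day 6 is stated, since they do not complete the window.
- Later events are shown separately: diary events on days 8-14 for the day-0 vaccine, and all events to day 28 for every vaccine, each labelled by source (diary or visit history).
- The by-group summary stays, with recording time per arm printed beside it.

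The protocol should also say whether group 6 keeps a card from visit 6, since the text and Table 1.2 can be read differently.

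Extending the MVA85A card only for participants still to be boosted is not advised. It would create two diary lengths among 30 people, possibly aligned with enrolment before or after the lockdown and with the boost interval.

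The cost is one additional table and a few lines of analysis wording, with no new visits, forms or samples. The downside is that late local reactions to BCG, which Section 5.4.1 leads one to expect, appear in the separate table and not in the main comparison.

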9. INVESTIGATIONAL PRODUCTS

9.1. ChAdOx1 85A

9.1.1. ChAdOx1 85A Description

ChAdOx1 85A is a new adenoviral vaccine vector (ChAdOx1) based on a chimpanzee adenovirus isolate Y25 expressing M. tb antigen 85A. ChAdOx1 85A is a replication defective adenovirus where the E1 locus, required for viral replication has been deleted. This virus can therefore be propagated easily with good yields in cell lines expressing E1 from AdHu5 such as human embryonic kidney cells 293 (HEK 293). ChAdOx1 85A also encodes almost the complete M. tb gene for Ag85A.

9.1.2. Supply and Storage of ChAdOx1 85A

ChAdOx1 85A is manufactured under Good Manufacturing Practice conditions at the Clinical Biomanufacturing Facility (CBF), University of Oxford. The vaccine is supplied as a liquid in glass vials for intramuscular administration and is stored at -80°C, in a locked, alarmed, temperature monitored freezer at the CCVTM, University of Oxford.

ChAdOx 85A will be shipped from CBF directly to the UVRI on dry ice and in the presence of a temperature logger. The vaccine will be certified and labelled for use in trial TB042 by a qualified person (QP) at CBF.

The vaccine will be stored at -80°C (nominal temperature) in a secure, temperature-monitored freezer at UVRI.

All movements of the study vaccine between the CBF and UVRI will be documented. Vaccine accountability, storage, shipment and handling will be in accordance with our vaccine related SOPs and associated forms.

9.1.3. Formulation of ChAdOx1 85A

The ChAdOx1 85A vaccine is formulated in formulation buffer at a concentration of 1.74×10^{11} vp/ mL. The formulation buffer consists of 10mM Histidine, 7.5% sucrose, 35mM NaCl, 1mM MgCl₂, 0.1% PS80, 0.1mM EDTA, 0.5% EtOH, pH 6.6. The fill volume is 0.5 mL.

9.1.4. Dispensing and administration of ChAdOx1 85A

All movements of vials of the trial vaccine between the CBF and UVRI, and in or out of the locked freezers, will be documented. On vaccination day, vaccines will be allowed to thaw to room temperature and will be administered within 1 hour. The vaccine will be administered intramuscularly over the deltoid region of the non-dominant upper arm, according to the standardized SOP. Subjects will stay in the unit for 60 minutes (± 10 minutes) after vaccination. During the administration of the vaccine, monitoring equipment, oxygen, medicines including bronchodilators and resuscitation equipment will be immediately available for the management of anaphylaxis and bronchospasm.

In order to minimise dissemination of the recombinant vectored vaccine virus into the environment, a number of measures will be instituted during and following vaccination:

- The intramuscular injection site will be covered with a dressing after vaccination to absorb any virus that may leak out through the needle track. The dressing will be removed from the injection site after 30 minutes.
- The dilution process will be carried out in a sealed vial in accordance with the standardized SOP.
- All disposable items including needles, vials, dressings, and protective clothing will be disposed of as GMO waste by autoclaving, in accordance with the current approved SOPs and standard practice.

9.2. MVA85A

9.2.1. MVA85A Description

The MVA85A vaccine consists of the attenuated vaccinia virus MVA vector with a 1176 base-pair insert, which is almost the complete *M.tb* gene for Ag85A, with the tissue plasminogen activator (TPA) signal sequence preceding the N terminus and a monoclonal antibody tag (pk) at the C terminus. Expression of the antigen 85A DNA sequence is regulated by the vaccinia P7.5 early/late promoter. MVA85A is manufactured under Good Manufacturing Practice conditions by IDT Biologika GmbH (IDT), Germany.

9.2.2. Formulation of MVA85A

MVA85A is supplied as a sterile liquid in glass vials. Each vial of lot 0050811 contains 400 μ L of vaccine at a concentration of 8.4×10^8 pfu/mL in 10mM Tris buffer 140 mM NaCl; pH 7.7. The dose of MVA85A to be used is 1×10^8 pfu.

9.2.3. Storage of MVA85A

MVA85A will be shipped from IDT directly to the UVRI on dry ice and in the presence of a temperature logger. The vaccine will be certified and labelled for use in trial TB042 by a qualified person (QP) at IDT.

The vaccine will be stored at -80°C (nominal temperature) in a secure, temperature-monitored freezer at UVRI.

All movements of the study vaccine between IDT and UVRI will be documented. Vaccine accountability, storage, shipment and handling will be in accordance with our vaccine related SOPs and associated forms.

9.2.4. Dispensing and administration of MVA85A

All movements of vials of the trial vaccine between IDT/CBF and UVRI and in or out of the locked freezer will be documented. Vaccine accountability, storage, shipment and handling will be in accordance with local SOPs and other relevant local forms.

On vaccination day, vaccines will be allowed to thaw to room temperature and will be administered within 1 hour. The vaccine will be administered IM over the deltoid region of the non-dominant upper arm, according to the site-specific SOP. Volunteers will stay in the unit for 60 minutes (± 10 minutes) after vaccination. During the administration of the vaccine, monitoring equipment, oxygen, medicines including bronchodilators and resuscitation equipment will be immediately available for the management of anaphylaxis and bronchospasm according to the site-specific SOP.

In order to minimise dissemination of the recombinant vectored vaccine virus into the environment, a number of measures will be instituted during and following vaccination:

- The dilution process will be carried out in a sealed vial in accordance with the vaccine dilution SOP.
- The IM injection site will be covered with a dressing after vaccination to absorb any virus that may leak out through the needle track. The dressing will be removed from the injection site after 30 minutes and will be disposed as GMO waste by autoclaving.
- All disposable items including nebuliser parts, needles, vials, dressings, and protective clothing will be disposed of as GMO waste by autoclaving, in accordance with the current approved SOP and standard practice.

